6.3.2 Clinical Response Definitions

6.3.2.1 Clinical Response at the EOT and TOC Assessments

Clinical outcome assessments (see [Table 5](#)) will be made by the Principal Investigator at the EOT and TOC visits. Clinical response will be classified as cure, failure, or indeterminate based on clinical outcome. A favourable clinical response is “clinical cure”. A clinical failure occurring at an earlier time point will be carried forward to the TOC visit.

Table 5 Clinical Response Assessments at the EOT and TOC Visits

Outcome	Definition
Clinical Cure	Total resolution of all signs and symptoms of pneumonia (ie, CABP), or improvement ^a to such an extent that further antimicrobial therapy is not necessary
Clinical Failure ^b	Any of the following: * Persistence, incomplete clinical resolution, or worsening in signs and symptoms of CABP that requires alternative antimicrobial therapy * Treatment-limiting AE leading to discontinuation of the study treatment regimen, when patient required alternative antimicrobial therapy to treat the pneumonia * Death wherein pneumonia (ie, CABP) is considered causative
Indeterminate	Study data are not available for evaluation of efficacy, for any reason including treatment change prior to completing at least 48 hours of the study treatment regimen; death wherein pneumonia is clearly non-contributory, lost to follow-up, or extenuating circumstances preclude classification as a cure or failure

^a Clinical improvement includes the absence of fever (temperature $\leq 38^{\circ}\text{C}$ oral or $\leq 38.5^{\circ}\text{C}$ rectally or tympanically) for at least 24 continuous hours, with temperature recorded twice daily, in addition to a substantial improvement in signs and symptoms of CABP. Substantial improvement includes a return to pre-CABP baseline levels for patients with decreased pulmonary function (eg, patients with chronic obstructive pulmonary disease).

^b Clinical failures at EOT are carried forward to TOC.

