12.1.1.4 Clinically Evaluable (CE) Population

The CE Population will be a subset of the MITT Population and will include patients who meet the minimal disease criteria for CABP and all evaluability criteria, including patients

who received at least the pre-specified minimal amount of the intended-dose and duration of study drug therapy, for whom sufficient information regarding the infection is available to determine the patient's outcome, and for whom there are no confounding factors that interfere with the assessment of that outcome; patients with an atypical pathogen as a sole causative pathogen of the infection will be excluded from the CE Population.

In addition to meeting the above criteria, patients must meet the following specific conditions:

- At least 48 hours of study drug therapy received in order to be considered an evaluable clinical failure, unless deemed a clinical failure based on a treatment-limiting AE
- At least 72 hours of study drug therapy received in order to be considered an evaluable clinical cure
- At least 80% of the intended doses of study drug therapy received. Compliance is determined as the total number of received doses divided by the total number of intended doses based on the first and last date and time of study drug administration
- Clinical response assessment at TOC (8 - 15 days after EOT), or a clinical failure at EOT or at any time up to 15 days after EOT is allowed. For patients who died a 28 day window up to and including 28 days after EOT is allowed
- A patient with an indeterminate response at TOC is not included in the CE population unless the reason for the indeterminate response is "Death where CABP is non causative"
- Did not receive more than one dose of an alternative (non-study) systemic antimicrobial that was potentially effective for the treatment of CABP, for a reason other than treatment failure.

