12.2.2.2 Secondary efficacy endpoints

For each secondary efficacy outcome measure listed in [Table 10](#), a two-sided 95% CI for the difference between cure, success and favourable outcome rates (ceftaroline minus ceftriaxone) will be computed using the method proposed for stratified designs by Miettinen and Nurminen ([Miettinen O et al 1985](#)). Cochran-Mantel-Haenzel weights will be used for the stratum weights (defined by district) in the calculation of the CI.

Per-Patient Clinical Cure Rate at the TOC Visit in the MITT, mMITT and ME Populations

The per-patient clinical cure rate at the TOC visit in the MITT and mMITT Populations will be determined as:

$$\frac{\text{Number of patients with outcome=clinical cure}}{(\text{Number of patients with clinical cure} + \text{Number of patients with clinical failure} + \text{Number of patients with indeterminate})}$$

By definition, patients in the ME Population must have sufficient information for the determination of clinical outcome. Thus, the per-patient clinical cure rate in the ME Population is defined as:

$$\frac{\text{Number of patients with clinical cure}}{(\text{Number of patients with clinical cure} + \text{Number of patients with clinical failure})}$$

The number and percentage of patients classified as clinical cure, clinical failure, or indeterminate (by definition, indeterminates are excluded from the ME population) will be tabulated for both treatment groups.

A two-sided 95% CI for the difference in clinical cure rates (ceftaroline minus ceftriaxone) will be computed using the method proposed for stratified designs by Miettinen and Nurminen ([Miettinen O et al 1985](#)). Cochran-Mantel-Haenzel weights will be used for the stratum weights (defined by district) in the calculation of the CI.

Per-Patient Clinical Cure Rate at the EOT Visit in the MITT and CE Populations

The per-patient clinical cure rate at the EOT visit in the MITT and CE Populations will be determined to support the findings at the TOC visit. The number and percentage of patients classified as clinical cure, clinical failure, or indeterminate (by definition, indeterminates are excluded from the CE Population) will be tabulated for both treatment groups.

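### The CE set used for the EOT cure rate is defined by TOC follow-up, which removes most EOT cures without a usable TOC response but keeps EOT failures

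*Protocol*

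**What the plan says.** Protocol 12.2.2.2 plans this secondary analysis: "The per-patient clinical cure rate at the EOT visit in the MITT and CE Populations will be determined to support the findings" at TOC, with a stratified two-sided 95% CI for the difference. Table 10 lists the same endpoint in MITT and CE.

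Protocol 12.1.1.4 defines one CE Population and no visit-specific version. Its follow-up condition reads "Clinical response assessment at TOC (8 - 15 days after EOT), or a clinical failure at EOT". A later failure also counts if it comes within 15 days of EOT, and the window is extended to 28 days after EOT for patients who died. It adds "A patient with an indeterminate response at TOC is not included in the CE population unless the reason for the indeterminate response is" a death not caused by the pneumonia.

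Table 5 (6.3.2.1) says which patients count as indeterminate, including "death wherein pneumonia is clearly non-contributory, lost to follow-up, or extenuating circumstances preclude classification as a cure or failure". Its footnote says "Clinical failures at EOT are carried forward to TOC".

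On the EOT analysis, 12.2.2.2 remarks that "by definition, indeterminates are excluded from the CE Population". The exclusion in 12.1.1.4, however, names only an indeterminate response at TOC. It sets no condition on the EOT response itself.

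**The concern.** Take two patients who meet every other CE criterion, complete the EOT assessment and are then lost. One was a failure at EOT and the other a cure. The failure is carried forward and stays in CE. The cure becomes indeterminate at TOC and leaves CE. Both had a known EOT outcome, yet only the failure is counted in the EOT rate.

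Membership of the EOT denominator therefore depends on the EOT outcome and on follow-up that comes 8-15 days later. The endpoint is meant to support the TOC result, but its CE version is conditioned on TOC follow-up. If follow-up after EOT differed between arms, part of that difference would appear as a treatment difference at EOT.

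**Working it through.** **Plan's own figure.** Inputs from Protocol 12.3 and 12.2: cure rate 85% in each arm (CE, TOC), margin 10%, power 90%, two-sided 95% CI, evaluability 77.5%. Evaluable patients per arm = (1.960 + 1.282)² × 2 × 0.85 × 0.15 / 0.10² = 267.9, so 268. Then 268 / 0.775 = 345.8, so 346 per arm and 692 in total, as stated. The sample size is not in question.

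**Who is in CE, by EOT outcome (all other criteria met).**

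| EOT outcome | After EOT | In CE? |
|---|---|---|
| Failure | No TOC visit | Yes, carried forward |
| Cure | Cure or failure at TOC, in window | Yes |
| Cure | Failure within 15 days after EOT | Yes |
| Cure | Death covered by the 28-day window or the non-causative-death exception | Yes |
| Cure | Lost, out of window or otherwise indeterminate at TOC | No |

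**Model for the TOC-follow-up rule.** Let p be the EOT cure rate among otherwise evaluable patients, and m the share of EOT cures in the last row of the table. All EOT failures are kept, so

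CE rate at EOT = p(1 − m) / [p(1 − m) + (1 − p)].

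The protocol gives neither p nor m. I assume p = 85% (the planning rate for TOC) to 90%, and m = 2%, 5% and 10%.

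| m | p = 85% | Shift (points) | p = 90% | Shift (points) |
|---|---|---|---|---|
| 2% | 84.7% | −0.3 | 89.8% | −0.2 |
| 5% | 84.3% | −0.7 | 89.5% | −0.5 |
| 10% | 83.6% | −1.4 | 89.0% | −1.0 |

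In counts, take 346 otherwise evaluable patients as an illustration: 294 cures and 52 failures (85.0%). If 29 cures (10%) have no usable TOC response, the rate is 265 / 317 = 83.6%.

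**Effect on the between-arm difference.**
- 85% in both arms, equal m: difference 0, unchanged.
- 85% in both arms, m = 5% against 10%: 84.33% against 83.61%, an artefact of about 0.7 points. At 90% it is 89.53% against 89.01%, about 0.5 points.
- 80% against 85%, m = 10% in both: 0.72/0.92 − 0.765/0.915 = 78.26% − 83.61% = −5.35 points instead of −5.00.

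**A CE rule that acts the other way.** Section 12.1.1.4 also drops failures with under 48 hours of therapy unless they rest on a treatment-limiting AE. Let e be the share of failures so dropped. With p = 85%, m = 5% and e = 5%, the rate is 0.8075 / (0.8075 + 0.1425) = 85.0%, so the two effects cancel. With e = 10% it is 0.8075 / (0.8075 + 0.1350) = 85.7%.

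**The case against.** Using one CE set at both visits is a defensible choice. It shows the same patients at EOT and TOC over a common denominator, which suits an analysis meant to support the TOC result. The EOT rate is also reported in MITT, which has no TOC requirement, so a result free of this selection stands beside the CE one. The trial is double-blind, and Protocol 5.8 asks patients who stop drug early to attend the later visits, so large or unequal losses are not expected. With 268 evaluable patients per arm at 85%, the simple 95% half-width for the difference is 1.96 × √(2 × 0.85 × 0.15 / 268) = 6.0 points, well above the shifts shown here. All of this stands, and it limits the importance of the point. It does not remove the asymmetry. Nor is this a detail left to the SAP, because the protocol itself fixes both the set and its use at EOT.

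Three stronger readings are tempting, and the protocol does not support them.
- A reader might infer that an EOT cure enters CE only with a determinate in-window TOC assessment. Section 12.1.1.4 also keeps those who fail within 15 days and those covered by the death provisions.
- A reader might infer that the CE rate at EOT is too low overall. The downward sign belongs to the TOC-follow-up rule, measured against otherwise evaluable patients. Against all treated patients the net sign is not fixed, because the 48-hour rule pushes upward.
- A reader might treat the whole planned non-evaluable share of 22.5% as lost EOT cures, which at p = 85% gives 81.4%, a shift of −3.6 points. That allowance must also cover patients failing the minimal disease criteria, sole atypical pathogens, short exposure, under-dosing and non-study antimicrobials. The protocol likewise gives no basis for assuming a wide gap in losses between arms.

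**Conclusion.** The point holds as a modest flaw in a supportive secondary analysis. The CE set is defined by TOC evaluability and reused at EOT, so selection into the EOT rate depends on the EOT outcome and on later follow-up. The direction of this component follows from the definitions alone. Its size rests on two quantities that the protocol does not give, the EOT cure rate and the share of EOT cures without a usable TOC response. Over the assumed ranges it is about 0.2 to 1.4 points per arm. For equal cure rates, the treatment difference moves only if losses differ between arms. The primary TOC analysis, the non-inferiority conclusion and the MITT analysis at EOT are not affected. This is a cheap improvement worth making, not a threat to the trial's conclusion.

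**What to change.** In Protocol 12.1.1.4, add a CE-at-EOT set. It should apply the same minimal-disease, exposure (48/72 hours), 80%-dose and non-study-antimicrobial criteria up to EOT, require an EOT response of cure or failure, and carry no TOC requirement. The cut-off at EOT should be written out, because the antimicrobial criterion now has no stated end date. Requiring a determinate EOT response would also make the remark that indeterminates are excluded true for this visit.

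Use the new set for the EOT cure rate in 12.2.2.2 and Table 10. Keep the TOC-based CE set unchanged for the primary endpoint and, at EOT, as a sensitivity analysis.

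The cost is one extra population flag from data already collected, and wording changes in three places. The sample size does not change. The downside is that the EOT and TOC rates will have slightly different denominators, which the retained sensitivity analysis lets the reader bridge.

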- Per-patient microbiological re-infection or recurrence rate at the LFU visit in patients in the ME Population who had a favourable microbiological outcome at the TOC visit

Safety in MITT Population:

- Adverse events (AEs)
- Electrocardiogram (ECG)
- Laboratory assessments
- Physical examinations

- Vital signs

Exploratory endpoint

- PK parameters derived from population PK analysis, and potential PK/PD relationships (will be reported separately)
- Length of hospital stay as measured at LFU visit
- Admission to an Intensive Care Unit as measure at LFU visit
- CAP-SYM 18 scores at baseline, day 2, 4, EOT, TOC and LFU visit

Statistical methods

The sample size for this study has been based on the primary outcome variable of clinical cure rate at the TOC visit in the CE Population. Assuming a point estimate for the clinical cure rate of 85% in the ceftriaxone treatment group, and 85% in the ceftaroline group in the CE Population, a non-inferiority margin of 10%, a power of 90%, and a 77.5% evaluability rate, a total sample size of 692 patients is required (346 patients in each treatment group).

The primary objective of this study is to determine the non-inferiority in the clinical cure rate for ceftaroline compared to that for ceftriaxone at the TOC visit in the CE Population in adult patients with CABP. A two-sided 95% confidence interval (CI) for the observed difference in the cure rate (ceftaroline group minus ceftriaxone group) will be computed using the method proposed for stratified designs by Miettinen and Nurminen ([Miettinen O et al 1985](#)). Cochran-Mantel-Haenzel weights will be used for the stratum weights (defined by district) in the calculation of the CI. This method corresponds to the expanded Farrington-Manning test ([Farrington CP and Manning G 1990](#)) for stratified designs with Cochran-Mantel-Haenzel weights. Non-inferiority of ceftaroline will be concluded if the lower limit of the 95% CI is -10% or higher.

If the clinical cure rates for ceftaroline are higher than that seen in ceftriaxone group and non-inferiority has been established in CE Population, a test of superiority will be conducted in the CE and MITT populations. Superiority of ceftaroline will be concluded if the two-sided p-value is less than 0.05 in both the CE and MITT populations.

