6.3 Efficacy

6.3.1 Microbiological Assessments of CABP

6.3.1.1 Sputum Samples for Culture

Obtain adequate sputum samples for culture, Gram's staining, and susceptibility testing at baseline, during the study drug period (Study Day 1 up to Day 7) if medically indicated; at the EOT and TOC visits, if the patient is deemed a clinical failure or if medically indicated; and at the LFU visit if medically indicated and the patient is relapsing. Sputum samples are not obtained at the TOC or LFU visits if the patient was previously deemed a failure. Sputum induction (eg, via nebulisation) should be performed by appropriately trained personnel (eg, a respiratory therapist), if medically indicated. Attempts to collect an adequate sputum sample may be repeated if appropriate. Perform culture and susceptibility testing at the local laboratory and send all isolates that are not contaminants (see list below) to the central laboratory for confirmation of organism identity and susceptibility.

The following organisms are considered sputum contaminants, rather than primary pathogens of CABP, and should not be sent to the central laboratory for confirmation of organism identity and susceptibility:

- Fungi (yeast and molds, eg, *Candida spp.* and *Aspergillus spp.*), unless there is evidence of a secondary fungal infection
- *Enterococcus spp.* or Group D *streptococci*
- *Viridans streptococci*
- *Coagulase-negative staphylococci*
- *Micrococcus spp.*
- *Neisseria spp.* other than *N. meningitidis* and *N. gonorrhoeae*
- *Corynebacterium spp.* and other coryneforms
- *Lactobacillus spp.*
- *Vibrio spp.*
- *Capnocytophaga spp.*
- *Cardiobacterium spp.*
- *Flavobacterium spp.*

Susceptibility testing of all isolates sent to the central laboratory will be performed by broth microdilution tests (to determine the MIC) and Clinical Laboratory Standards Institute (CLSI)

disk diffusion tests. Refer to the Laboratory Manual for specific procedures pertaining to the collection, processing, storage, and shipment of sputum cultures.

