6.3.1.3 Blood Samples for Culture

Obtain blood for culture at baseline and as medically indicated from Study Day 1 to the TOC visit. Repeat blood cultures upon receipt of a positive result (rather than daily) until sterilization is confirmed in those patients with a positive result at baseline (ie, baseline blood culture grows an organism other than those judged to be transient or resident skin flora). Obtain blood for culture at the LFU visit only if medically indicated and the patient is experiencing clinical relapse. Blood for culture is not obtained at the TOC or LFU visits if the patient was previously deemed a failure.

When blood cultures are required, obtain one aerobic bottle and one anaerobic bottle from two separate sites for a total of four bottles. Perform culture and susceptibility testing at the local laboratory and send isolates, other than those judged to be transient or resident skin flora, to the central laboratory for confirmation of organism identity and susceptibility. Susceptibility testing of all isolates sent to the central laboratory will be performed by broth microdilution tests and CLSI disk diffusion tests.

Refer to the Laboratory Manual for specific procedures pertaining to the collection, processing, storage, and shipment of blood cultures.

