6.3.4 Microbiological Response Definitions

6.3.4.1 Per-Pathogen Microbiological Response

A microbiological outcome at the TOC visit will be determined in the mMITT and ME populations for each pathogen isolated at baseline (see

[Table 7](#)). Microbiological outcome categories are eradication, presumed eradication, persistence, presumed persistence, and indeterminate, as defined in the table below. Favourable microbiological outcomes are eradication or presumed eradication. Unfavourable microbiological outcomes are persistence or presumed persistence.

Table 7 Microbiological Outcome Categories

Outcome ^a	Definition	
Favourable	Eradication	An adequate source specimen ^b demonstrates absence of the original baseline pathogen.
	Presumed eradication	An adequate source specimen ^b was not available to culture and the patient was assessed as a clinical cure.
Unfavourable	Persistence	Source specimen demonstrates continued presence of the original baseline pathogen.
	Presumed persistence	An adequate source specimen ^b was not available to culture and the patient was assessed as a clinical failure.
Indeterminate	Indeterminate	An adequate source specimen ^b was not available to culture and the patient's clinical response was assessed as indeterminate.

^a The microbiological outcomes at TOC are only applicable to patients who are not clinical failures at EOT. Patients who are failures at EOT will have the corresponding microbiological outcome determined from EOT cultures and carried forward to TOC. If no EOT culture is available for patients who are clinical failures at EOT, then the microbiological outcome at TOC will be presumed persistence. Otherwise, the microbiological outcome at TOC will be determined from cultures obtained at the TOC visit window. If no culture is available in the TOC window then the microbiological outcome at TOC will be presumed from the clinical response (see [Table 5](#)) at TOC.

^b An adequate source specimen is defined as any sample that may yield the growth of a CABP pathogen eg, blood, respiratory specimens, or pleural fluid.

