6.3.4.3 Microbiological Categories for Pathogens Identified After Baseline Assessment

Microbiological categories for pathogens identified after the baseline assessment are super-infection, new infection, colonization, and re-infection or recurrence, as defined in [Table 8](#).

Table 8 Categorization of Bacterial Pathogens Identified After Baseline Assessment

Super-infection	Isolation of a new pathogen(s) (other than the original baseline pathogen(s)) during the period up to and including EOT from cultures of the original CABP, or a new CABP at the same site, regardless of susceptibility to study drugs, in a patient who has signs and symptoms of infection requiring alternative antimicrobial therapy.
New Infection	Isolation of a new pathogen (other than the original baseline pathogen) determined at TOC or LFU regardless of susceptibility to study drugs, in a patient who has signs and symptoms of infection requiring alternative antimicrobial therapy
Colonization	Isolation of an organism from the original CABP site that is not associated with signs and symptoms of active infection and does not require antimicrobial therapy. Colonization will be determined only at EOT and TOC when an assessment of clinical response is performed.
Microbiologic re-infection or recurrence	Isolation of a baseline pathogen from the original CABP site, at the LFU visit, in patients who had favourable clinical and microbiological responses at TOC. To be defined as a recurrent infection, pathogens must be associated with emergence or worsening of clinical signs and symptoms, with or without laboratory evidence of active infection, and require antimicrobial therapy.

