12.1.1.5 Microbiologically Evaluable (ME) Population

The ME Population includes patients who meet criteria for both the CE (Section 12.1.1.4) and mMITT (Section 12.1.1.3) Populations.

At the TOC visit, the Principal Investigator will collect a microbiology specimen from blood, sputum, and pleural fluid samples only if medically indicated. Hence, many or most patients will not have a TOC microbiology specimen available for analysis. If a suitable specimen cannot be collected, the per-pathogen microbiological outcome will be "presumed eradicated" or "presumed persistent" based on the clinical response.

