Per-Patient Microbiological Re-infection/Recurrence Rate at the LFU Visit

This analysis will be performed in the subset of patients in the ME Population who had a favourable microbiological outcome at the TOC visit. The number and percentage of patients in each treatment group that have a re-infection or recurrence at the LFU visit will be tabulated.

Two-sided 95% CI for the difference in re-infection/recurrence rates (ceftaroline minus ceftriaxone) will be constructed using the method proposed for stratified designs by Miettinen and Nurminen (Miettinen O et al 1985). Cochran-Mantel-Haenzel weights will be used for the stratum weights (defined by district) in the calculation of the CI.

Table 10 Secondary Efficacy Endpoints

Population	Subset(s)	Assessment	Per-patient Evaluation	Outcomes
MITT, mMITT and ME		TOC	Clinical response	Cure Failure Indeterminate (MITT and mMITT)
MITT and CE		EOT	Clinical response	Cure Failure Indeterminate (MITT only)
mMITT and ME		TOC	Microbiological response	Favourable: eradication or presumed eradication Unfavourable: persistence, presumed persistence, or indeterminate (mMITT only)

Population	Subset(s)	Assessment	Per-patient Evaluation	Outcomes
MITT and CE		TOC	Overall response	Success: clinical cure and either a radiographic success or radiographic indeterminate Failure: either clinical failure or clinical indeterminate, or radiographic failure
mMITT and ME	Per pathogen	TOC	Clinical response	Cure Failure Indeterminate (mMITT only)
mMITT and ME	Per pathogen	TOC	Microbiological response	Favourable: eradication or presumed eradication Unfavourable: persistence, presumed persistence, or indeterminate (mMITT only)
CE	Clinically cured at TOC	LFU	Clinical response	Continued response Relapse
ME	Micro-biologically favourable outcome at TOC	LFU	Microbiological re-infection / recurrence	No re-infection or recurrence Re-infection or recurrence

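### The LFU re-infection/recurrence denominator omits the clinical-cure condition that Table 8 puts on the event, so culture-negative clinical failures are counted as free of recurrence (minor)

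*Protocol*

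**What the plan says.** **Denominator.** Section 12.2.2.2 of the Protocol states: "This analysis will be performed in the subset of patients in the ME Population who had a favourable microbiological outcome at the TOC visit". The synopsis list of secondary endpoints counts the event "in patients in the ME Population who had a favourable microbiological outcome at the TOC visit", and Table 10 gives the same subset. None of the three mentions clinical response. Table 10 allows two outcomes for this endpoint, event or no event, with no indeterminate category.

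**Event.** Table 8 (section 6.3.4.3) defines microbiological re-infection or recurrence as isolation of a baseline pathogen at LFU "in patients who had favourable clinical and microbiological responses at TOC". Both responses must be favourable.

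**How a clinical failure can be microbiologically favourable.** In Table 7 (section 6.3.4.1), eradication requires only that an adequate specimen "demonstrates absence of the original baseline pathogen". Footnote a adds: "Patients who are failures at EOT will have the corresponding microbiological outcome determined from EOT cultures and carried forward to TOC". Clinical failures can belong to the ME population: "The ME Population includes patients who meet criteria for both the CE (Section 12.1.1.4) and mMITT (Section 12.1.1.3) Populations", and the ME cure rate in section 12.2.2.2 has failures in its denominator.

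**Sampling at LFU.** Section 6.3.1.1: "Sputum samples are not obtained at the TOC or LFU visits if the patient was previously deemed a failure". Section 6.3.1.3: "Blood for culture is not obtained at the TOC or LFU visits if the patient was previously deemed a failure".

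**The concern.** A recurrence rate is readable when everyone in the denominator could have had the event. Here the numerator requires clinical success at TOC and the denominator does not. Patients who have already failed clinically, but whose culture was clean, are in effect recorded as good LFU results. That lowers the reported rate in any arm that has such patients, and it could shift the between-arm difference if the arms have different proportions of them.

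The protocol also gives two definitions from which two programmers could build different denominators for a pre-specified secondary endpoint with a between-arm confidence interval. The parallel clinical endpoint avoids this: section 12.2.2.2 limits the relapse rate to CE patients who were a clinical cure at TOC.

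**Working it through.** **1. The plan's own figure.** The protocol states no figure for this endpoint. Its sample size can be reproduced from section 12.3 (85% cure in both arms, margin 10%, power 90%, evaluability 77.5%) and the two-sided 95% interval in section 12.2:

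- n per arm = (1.960 + 1.282)² × 2 × 0.85 × 0.15 / 0.10² = 267.9, so 268 evaluable
- 268 / 0.775 = 345.8, so 346 per arm and 692 in total

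This matches the protocol and does not depend on the LFU endpoint.

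**2. Who is in the denominator but not at risk.**

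| ME clinical failure | Microbiological outcome at TOC | In denominator? | Can have the event (Table 8)? |
|---|---|---|---|
| Failure at EOT, EOT culture free of every baseline pathogen | Eradication, carried forward | Yes | No |
| Failure first declared at TOC, TOC culture free of every baseline pathogen | Eradication | Yes | No |
| Failure with no culture | Presumed persistence | No | No |
| Failure with pneumococcus found by urinary antigen only | Follows the clinical outcome | No | No |
| Failure with an atypical co-infection | Atypical follows the clinical outcome, so the patient is unfavourable (section 6.3.4.2) | No | No |

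Only the first two rows cause the problem. They are foreseeable, because Table 1 and Appendix H call for sputum and blood cultures when a patient is deemed a failure at EOT or TOC.

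**3. Share of the denominator not at risk.** Let c = 0.85 be the cure rate. This is the CE planning value, applied here to ME as an assumption. Let f be the share of ME clinical failures with culture-documented eradication, which the documents do not give. Take all ME cures as microbiologically favourable. Then

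share not at risk = (1 − c)f / [c + (1 − c)f]

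The reported rate equals the at-risk rate times one minus this share.

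| f (assumed) | Calculation | Not at risk | Understatement at an assumed 3% at-risk rate |
|---|---|---|---|
| 10% | 0.015 / 0.865 | 1.7% | 0.05 points |
| 25% | 0.0375 / 0.8875 | 4.2% | 0.13 points |
| 50% | 0.075 / 0.925 | 8.1% | 0.24 points |
| 100% (ceiling) | 0.15 / 1.00 | 15% | 0.45 points |

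The share does not depend on the size of the ME population.

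**4. Example in counts.** Assume a pathogen yield of 30%: 0.30 × 268 ≈ 80 ME patients per arm, 68 cures, 12 failures, and two events.

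- At-risk denominator: 2/68 = 2.94%
- As planned, f = 10%: 2/69 = 2.90%
- f = 25%: 2/71 = 2.82%
- f = 50%: 2/74 = 2.70%
- f = 100%: 2/80 = 2.50%

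**5. Effect on the between-arm difference.** Take the same 3% at-risk rate and the same 15% failure share in both arms:

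- f of 25% against 50%: 3% × (0.9577 − 0.9189) = 0.12 points
- f of 0% against 50%: 3% × (1 − 0.9189) = 0.24 points
- f of 0% against 100%: 3% × (1 − 0.85) = 0.45 points

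For scale, with about 70 patients per arm a simple 95% half-width is 1.96 × √(2 × 0.03 × 0.97 / 70) = 5.65 points. An artefact of 0.24 points is about 4% of that. If the not-at-risk share is the same in both arms, no spurious difference arises; any true difference shrinks by the same factor.

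**The case against.** The mismatch in the text is not in dispute. The case against concerns how much it matters, and most of it stands.

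- **The size is assumed.** The documents give neither the ME population size nor the share of failures that are culture-negative, so any percentage follows from the chosen f. Several rules shrink the group, as the table in the working shows.
- **The effect is small.** It is a few tenths of a percentage point at most, on a secondary endpoint with no margin or success rule of its own.
- **A reader might infer that the arm with worse clinical results will look better at LFU.** The documents do not support that as a general statement. It needs culture-negative failures to make up a larger part of one arm's denominator; more failures without a clean culture would not do it.
- **A reader might also infer that everyone wrongly counted has been switched to other antimicrobials.** Table 5 also classes deaths caused by the pneumonia as failures, so this is not true of all of them.
- **The sampling rules are supporting evidence only.** The bar on LFU specimens from earlier failures is explicit for sputum and blood, not for pleural fluid. Table 8 is what makes the event impossible.
- **The subset could be settled in the SAP.** That would usually dispose of a programming detail. Here, though, the protocol itself fixes both the event and the denominator, and they disagree. One could also say that three places agree and Table 8 is the exception, but then the event definition would need changing, and the protocol would still be inconsistent until that was done.

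**Conclusion.** The point holds as a minor inconsistency with a known direction. Followed exactly, the plan scores culture-negative clinical failures as having no re-infection or recurrence although Table 8 rules the event out for them, and nothing in the protocol removes them from the denominator.

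The understatement is 1.7–8.1% in relative terms for an assumed f of 10–50%, with a ceiling of 15%. This rests on the 85% planning cure rate carrying over to ME and on ME cures being microbiologically favourable. The absolute size also rests on the assumed 3% rate. Confidence is high in the mismatch and low in any particular magnitude. It would be wrong to read this as a bias that could change how the arms compare on efficacy.

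**What to change.** In the synopsis, section 12.2.2.2 and Table 10, define the subset for this endpoint as ME patients with clinical cure and a favourable microbiological outcome at TOC. That matches Table 8 and the construction of the parallel relapse endpoint. It should be settled before unblinding.

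The cost is one phrase in three places. No data collection, visit or procedure changes. The denominator becomes slightly smaller (in the example, 68 per arm instead of 69 to 74 for f of 10–50%), with a correspondingly small loss of precision.
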